NO Bioavailability: NOS vs. nitrate-nitrite pathways. It is widely known that the L-arginine-NOS system significantly contributes to the overall production of NO. Until recently the inorganic anions nitrite (NO_2^-) and nitrate (NO_3^-) were considered inert end products of NO metabolism. However, accumulating evidence suggests that NO_2^- and NO_3^- metabolism occurs in the blood and various tissues to form NO (4, 31, 32). Thus, nitrite reduction (i.e. nitrate-nitrite-NO pathway) represents an alternative and differentially regulated system for NO generation that operates in parallel to the classic L-arginine-NOS pathway (33). Therefore, increasing plasma NO_2^- and NO_3^- levels in older adults may enhance NO bioavailability and subsequently improve blood pressure responsiveness to physiological stressors that have previously been demonstrated to be altered with aging and/or involve NO mediated mechanisms.

Benefits of dietary nitrate supplementation: In recent years data have accumulated to suggest that dietary nitrate supplementation can have physiological and therapeutic effects. In healthy young humans acute oral nitrate supplementation improves exercise efficiency and tolerance (2, 3, 27, 28). Dietary nitrite also reverses age-associated vascular endothelial dysfunction and large artery stiffness in mice via restoration of NO bioavailability and reductions in oxidative stress and inflammation (47). Furthermore, a number of studies in animals have reported a protective effect of low dose nitrite against ischemia-reperfusion injuries to various organs (10, 15, 22, 26, 54). Interestingly, acute ingestion of dietary nitrate prevents endothelial dysfunction induced by an acute ischemic insult in the forearm of healthy humans (53). Acute (hours) and short term (1-3 days) dietary inorganic nitrate consumption has also been shown to have favorable effects on isolated measurements of resting blood pressure (BP) in healthy volunteers (23, 28, 29, 53). Additionally, chronic dietary nitrate supplementation can have a sustained effect on BP in rats (41). To our knowledge the medium term effects (4 weeks) of dietary nitrate supplementation on BP have not been examined in healthy adults. Moreover, the longer term effects (weeks to months) of dietary nitrate on vascular function and/or arterial stiffness in humans are unknown.

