Figure 1. Regression line used to determine chemosensitivity.

6. Metaboreflex test. Subjects will be studied while in the supine position under standardized conditions.

Maximal voluntary contraction (MVC) of the nondominant hand will be measured by having subjects squeeze a handgrip device at maximal effort three times; the average value will be used as the MVC. The MVC will be used to calculate a relative work rate of 30% MVC for the experimental protocol. Subjects will then rest quietly for 10 min after which an isometric handgrip test will be performed for 2 min. During the last 3 s of the isometric handgrip test, an occlusion cuff placed on the exercising arm above the elbow

will be rapidly inflated to suprasystolic pressure (240 mmHg) and remain inflated for 2 min and 15 s (post exercise ischemia, PEI). The additional 15 s of post exercise ischemia is incorporated to account for the potential effects of the initial decrease in BP that occurs when exercise is immediately stopped.

8. Rhythmic Forearm Exercise. Rhythmic forearm exercise will be conducted with a handgrip dynamometer at a light (~4 kg) and moderate (~8 kg) level of exercise (4 minutes each), as previously described (6). In addition, this technique has been adapted to facilitate beat-to-beat measurements of brachial artery blood flow via Doppler ultrasound.

9. Measurement of Forearm Blood Flow by Doppler Ultrasound. Forearm blood flow (FBF) will be determined from the simultaneous measures of brachial artery diameter and mean blood velocity (MBV). The echo-Doppler image of the brachial artery will be obtained in real time using a hand-held 12 MHz linear probe, operating in B-mode. The probe will be positioned over the brachial artery, approximately 9 cm proximal to the medial epicondyle. Brachial artery blood flow is the product of mean blood velocity and artery cross sectional area. Forearm vascular conductance (FVC) will be calculated using blood flow and mean arterial pressure

9. Cold Pressor Test. After 10 minutes of quiet rest, a 2-minute baseline period will be recorded, followed by immersion of the hand in ice water (0-4 degrees C) for 2 minutes. Heart rate and blood pressure will be averaged over each minute of cold immersion and recovery; these values will be compared to the average values during the pre-stress period.

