10. Plasma Nitrate/Nitrite and cGMP. Plasma nitrate and nitrite levels will be determined from blood samples using a Sievers chemiluminescence NO analyzer (NOA 280i; Sievers Instruments, Boulder, CO). $[\text{NO}_2^-]$ will be determined by addition of plasma samples to potassium iodide in acetic acid at room temperature in a gas-sealed purging vessel. To minimize the influence of diet on plasma levels of nitrate/nitrite and measurements of physiologic function, all subjects will be asked to follow a 3 day low nitrate diet prior to each study day. cGMP will be determined using an enzyme immunoassay (Cayman Chemical).

11. Dietary Nitrate Supplementation. At study entry, the 15 older subjects will be randomized to receive either a beetroot powder containing nitrate (active) or a beetroot powder without nitrate (placebo) (Neogenis Sport, Austin TX) for 4 weeks. After visit 2 and the subsequent 4-week washout period, all subjects will be crossed over to receive either the active or placebo powder (opposite of the one they received at study entry) for another 4 weeks (Figure. 2).

12. Data Analysis and Statistics.

Sample-size/ Statistical Power: The primary aim of this investigation is to assess the potential efficacy of dietary nitrate supplementation for improving physiologic function on blood pressure within older individuals. With this aim in mind, we have designed a randomized, double-blind crossover, placebo-controlled study to assess potential efficacy and provide preliminary data for designing a larger trial in the future. Thus the primary endpoint is the change from baseline to end of treatment in blood pressure responses to various physiological stressors in older individuals.

Data Analysis: The primary variable of interest for this investigation is blood pressure responses to physiological stressors which will be measured at baseline and at the end of each respective 4 week treatment (beetroot juice with nitrate vs. placebo) and analyzed

as change from baseline. For the primary analysis, the change in pressure response from baseline to end of treatment will be compared between treatment groups (beetroot juice with nitrate vs. placebo) using a two-way repeated measures analysis of variance (ANOVA). Exploratory analyses will be performed to assess whether improvements in BP are positively correlated with changes in indices of arterial stiffness and whether improvements in blood pressure responses are associated with changes in vascular function.

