[figure not shown]
PROTOCOL - To address Specific Aims

Rationale and hypothesis:

As humans age, nitric oxide bioavailability decreases and there is an elevation in resting sympathetic activity (17, 19). This increase contributes to increased arterial stiffness and blood pressure during rest and exercise. Blood pressure responsiveness is also increased due to many factors including a decrease in the sensitivity of pressure receptors located in the carotid arteries and aorta. Recent evidence has shown that acute and short term (days) dietary nitrate supplementation is potentially effective in increasing NO bioavailability (5, 23, 27) and has favorable effects on measures of peripheral blood pressure at rest (23, 24). We will examine whether longer durations of dietary nitrate supplementation (4 weeks) have favorable effects on blood pressure responsiveness to a variety of physiological stressors in older adults.

Approach:

15 healthy older subjects will be studied. All older adults will undergo 4 separate days of testing as well as the placebo/supplementation portion of the study (Figure 2). We will also recruit 10 young adults to serve as a control group to compare baseline (prior to any intervention) data between age groups. The young group will only participate in one day of testing and will not undergo any of the placebo/supplementation portions of this study. Each group on their respective testing days will be subjected to a battery of tests that include a blood draw, spontaneous baroreflex testing, two separate consecutive hypoxic ventilatory response tests, handgrip exercise (both isometric and rhythmic), and a cold pressor test. The older group after undergoing testing on visits 1 and 3 will then be given their placebo/supplementation beetroot packets to be consumed once per day for 4 weeks. On each study day, heart rate will be monitored by 3-lead ECG and beat-to-beat arterial pressure will be measured using a Nexfin device on the middle finger during each test. Arterial O₂ saturation levels will be monitored by pulse oximetry throughout the hypoxic ventilatory tests. A single venous blood draw will be performed at the start of each study day (Figure 3) for the determination of plasma nitrate and nitrite levels.

[figure not shown]

Figure 3. Experimental testing on each study day

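### Does the undefined term for vascular function in the exploratory analysis need a prespecified index, given that forearm flow and conductance could disagree?

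*Combined protocol and SAP*

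**What the plan says.** The relevant sentence is in Research Design and Methods, item 12 (Data Analysis). It lists two exploratory questions. One is "whether improvements in BP are positively correlated with changes in indices of arterial stiffness". The other is "whether improvements in blood pressure responses are associated with changes in vascular function". Stiffness therefore has its own question, and the Background also treats the two as distinct, saying that "the longer term effects (weeks to months) of dietary nitrate on vascular function and/or arterial stiffness in humans are unknown". Pulse wave velocity is not the evident meaning of vascular function.

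The limb vascular measures come from the Doppler recording. Under Rhythmic Forearm Exercise (item 8) the plan says "this technique has been adapted to facilitate beat-to-beat measurements of brachial artery blood flow via Doppler ultrasound", at a light and a moderate load. Under Measurement of Forearm Blood Flow (the first of two items numbered 9), flow is velocity times cross-sectional area, and "Forearm vascular conductance (FVC) will be calculated using blood flow and mean arterial pressure". Under Approach, "beat-to-beat arterial pressure will be measured using a Nexfin device on the middle finger during each test", so a pressure response exists for rhythmic exercise as well as for the other stressors.

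Nothing says which index, load, stressor or pressure component enters the association.

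**The concern.** Flow (FBF) does not contain MAP in its formula; conductance (FVC) does. If the pressure response is MAP from the recording that also supplies the divisor of FVC, the variable on one axis is built into the variable on the other. One subject with assumed values shows the effect. Exercise MAP falls from 110 to 100 mmHg and flow from 300 to 285 mL/min. Flow is down 5.0%, but conductance goes from 300/110 × 100 = 272.7 to 285/100 × 100 = 285.0 mL/min per 100 mmHg, up 4.5%.

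The worry is that, with 15 older subjects and the index chosen after the data are seen, one data set could be reported as showing a vascular mechanism or as showing none. The trial is meant to supply preliminary data for a larger one, so a mechanistic statement that depends on such a choice would be weak guidance.

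**Working it through.** **Inputs.** From the plan: n = 15 older subjects; FBF without MAP; FVC from flow and MAP. The formula for FVC is not printed, so FVC = FBF/MAP is assumed. The plan gives no SD, significance level or effect size, so these too are assumed: SD of the change in log MAP (m) 5%; residual SD of flow s = 10%, 15% or 20%; flow following pressure with slope a = 0, 0.5 or 1; two-sided 5% test, for which the critical |r| at n = 15 is 0.514; 40,000 simulated trials per setting.

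**Step 1: the tightest pairing.** On the log scale, change in FVC = change in FBF − m. Hence slope(FVC on m) = slope(FBF on m) − 1, and the signs differ when the flow slope lies between 0 and 1. With a = 0, the correlation of FVC with m is −0.05/√(0.05² + s²), which is −0.447, −0.316 and −0.243 for the three values of s, although flow itself is unrelated to pressure.

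**Step 2: the response as the plan appears to use the word.** The analysis concerns pressure responses. For the cold pressor test the plan compares stress values with the pre-stress average. On that pattern the variable is exercise minus rest, d = m − r, where r is the change in resting MAP. If m and r have equal SD σ and correlation ρ, then cov(m, d) = σ²(1 − ρ) and var(d) = 2σ²(1 − ρ). The expected slope difference between FBF and FVC is therefore 0.5 rather than 1, and it varies from one data set to another. With a = 0, s = 10% and ρ = 0.7, the induced correlation is −0.447 × √(0.3/2) = −0.173.

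**Step 3: simulated consequences** (ranges over a and s; ρ from 0.5 to 0.9 in the second row).

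| Pressure variable | FBF and FVC opposite in sign | Exactly one significant |
|---|---|---|
| Same MAP that divides flow | 32% to 63% | 11% to 40% |
| Exercise minus rest, indices at exercise level | 10% to 35% | 3% to 12% |
| Unrelated to both indices | 8% to 16% | 2% to 5% |

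With a = 0, FVC is significant in about 14% to 41% of trials in the first row and 5% to 13% in the second. If the pressure response comes from another stressor and its correlation with the rhythmic-exercise response is 0.5 (assumed), exactly one index is significant in 5% to 12%.

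**Step 4: a significant reversal.** With these inputs, both indices are significant in opposite directions in at most about 0.02% of trials. This can be made commoner only by assuming that flow varies as little as pressure: with both SDs at 8% and a flow–MAP correlation of 0.5, it reaches 15%. The usual disagreement is one index significant and the other not.

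**The case for a change.** The strongest case for a change is that the gap is real and cheap to close. The term is undefined, rhythmic handgrip is in the test battery with pressure recorded throughout, and the algebra in step 1 is exact for the pairing it describes. It is exact again if flow and conductance are themselves expressed as log change from rest, which the plan neither requires nor excludes. One added sentence could name the index, load and pressure component, and could take the tested pressure response from a different stressor.

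The missing definition and the algebra stand; the need for a change does not follow from them. The problem requires four choices together: vascular function read as a forearm index, pressure taken as MAP, the stressor taken as rhythmic exercise, and conductance formed by simple division and tested against its own divisor. The plan prescribes no such combination, and the other stressors lack the algebraic link. The proposed remedy also has a cost. Withholding a test of rhythmic-exercise pressure against its own recording would remove the most direct flow–pressure comparison, although FBF contains no MAP. If flow follows pressure while conductance does not, that is a physiological finding rather than an artefact of calculation. What remains useful, showing both indices and noting the shared term, is ordinary reporting practice.

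**Conclusion.** The wording is incomplete, but no change to the plan follows. No stated rule yields a wrong result; the plan leaves a gap in an exploratory analysis that a competent analyst fills by presenting flow and conductance side by side and pointing out that conductance carries MAP in its denominator. The high disagreement rates (32% to 63% opposite signs, 11% to 40% with one index significant) belong to one pairing. Under the exercise-minus-rest reading they fall to 10% to 35% and 3% to 12%, of which 8% to 16% and 2% to 5% would occur by chance with unrelated pressure. A significant reverse association is not realistic unless flow is as stable as pressure.

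All of these rates rest on assumed SDs, slopes and rest–exercise correlations, and on FVC = FBF/MAP. The primary two-way repeated measures ANOVA of the pressure responses uses neither index and is unaffected.

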Dietary Nitrate Supplementation and Physiological Function in Older Adults

NCT02593305

July 1, 2015

Blood pressure responsiveness in older adults following dietary nitrate supplementation.

Principal Investigator: [name].

Co-investigator(s): [name].

Abstract

1 in 3 adults in the U.S. have hypertension which is known to increase the risk of heart disease and stroke. Blood pressure regulation is mediated by many factors including but not limited to metabolic factors, pressure/stretch sensing receptors located in the aorta and carotid arteries, endothelial cell function, and kidney function (via water and sodium absorption/excretion). It has been shown that many of these regulatory mechanisms are altered and/or become dysfunctional with aging. Specifically older adults commonly demonstrate a decreased sensitivity in pressure receptors and/or endothelial dysfunction. Additionally with aging, there is an increase in sympathetic nervous system activity and arterial stiffness which can contribute to higher blood pressure. The important vasodilator, nitric oxide (NO), has been implicated as a key signaling molecule involved in several of the mechanisms in blood pressure regulation outlined above. A decreased NO production or bioavailability is thought to contribute to several of the physiologic changes that come with aging. Therefore, the overall aim of this study is to use a randomized, double-blind crossover, placebo controlled study to examine the effects of acute dietary nitrate supplementation (to boost bioavailable NO) on various parameters of blood pressure regulation and responsiveness in normal healthy older adults. Our main hypothesis is that 4 weeks of dietary nitrate supplementation will decrease the blood pressure responses in older adults in response to a variety of physiological stressors.

Research Plan

I. Specific Aims:

Specific Aim 1: Determine whether carotid chemoreceptor sensitivity is altered with healthy aging. We will measure heart rate, blood pressure, and ventilatory (minute ventilation) responses to acute hypoxia in young and older adults. We hypothesize carotid body chemosensitivity to hypoxia is augmented with healthy aging.

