A total of 25 normal healthy subjects will be recruited for this study. We will recruit 15 older (60-85 years of age) and 10 young (18-35 years of age) adults. The young subjects will serve as a control study group and will not participate in the intervention portion (i.e. dietary nitrate supplementation) of the study. Exclusion criteria include hypertension, hyperlipidemia, smoking, heart disease, diabetes, body mass index (BMI) ≥ 30 kg/m², autonomic disorders and other conditions or medications that might normally alter blood pressure responses. They will not be taking any medications except for oral contraceptives (in young women). Subjects who engage in rigorous physical exercise programs (greater than 45 minutes in duration and exceeding 3 times per week) will be excluded. Subjects that have an aversion to beets will also be excluded. Subjects will be pre-screened by telephone and a brief health history will be assessed. Young women will be studied in the early follicular phase of their menstrual cycle (or the low- hormone phase of oral contraceptive use), to minimize any effects of reproductive hormone status, which may make interpretation of results difficult. All females of child bearing potential will have a negative pregnancy test before starting the study. Recruitment will consist of a University-wide email to students, faculty, staff, and retired faculty.

Experimental Procedures:

1. ***Subject Monitoring.*** Heart rate will be monitored by 3-lead ECG. Beat-to-beat arterial pressure will be measured using a Nexfin device placed on the middle finger. Respiratory rate and tidal volumes will be measured by turbine (flow-volume turbine, Vacumetrics). End-tidal CO₂ and inspired O₂ will be measured by capnography.

2. ***Venipuncture and Blood Draw.*** Single venous blood samples (~15-20 mL) from an antecubital vein using aseptic technique will be obtained on each study day for determination of nitric oxide metabolites (nitrate and nitrite) and cGMP. Fasting glucose and lipid concentrations will be determined from the blood sample obtained on the first study day.

[figure not shown]
3. ***Applanation Tonometry.*** High-fidelity radial artery pressure waveforms will be recorded by applanation tonometry of the radial pulse in the right wrist using a “pencil type” micromanometer (Millar Instruments, Houston, Texas). The radial blood pressure

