(BP) and waveforms will be calibrated from the systolic and diastolic brachial artery BP (cuff). A validated, generalized transfer function will be used to generate the corresponding aortic pressure waveform (SphygmoCor system, AtCor Medical, Sydney, Australia). Additionally, ECG gated arterial waveforms will be obtained from the carotid and femoral arteries. Pulse wave velocity (PWV; index of arterial stiffness) will be determined using the SphygmoCor PVX system. The time (t) between the feet of recorded pressure waves will be determined as the mean of 10 consecutive cardiac cycles. PWV is calculated by the system software from the distance (D ; meters) between measurement points and the measured time delay (t): $PWV = D/\Delta t$ (m/s).

4. Spontaneous Baroreflex Test. Heart rate will be measured via ECG and matched to beat-to-beat arterial pressure recording over a 10-minute resting period. Respiratory rate and tidal volume will be measured during this time to determine the influence of respiratory rate and volume on heart rate. Computer software will be used to determine all sequences of three or more successive heart beats in which there are concordant increases or decreases in systolic BP and RR interval. A linear regression will be applied to each of the sequences, and an average regression slope calculated for the sequences detected during each recording period. This slope represents the cardiac baroreflex sensitivity (in milliseconds per millimeter of mercury) by the spontaneous baroreflex method (SBR slope).

5. Hypoxic ventilatory response. The sensitivity of the carotid body chemoreceptors will be assessed using a hypoxic ventilatory response test (completed in duplicate, separated by a minimum of 15 minutes of quiet normoxic breathing). End-tidal CO₂ levels will be clamped at eupneic values throughout hypoxia by using a partial rebreathe system. Hypoxia will be achieved by titrating the level of inspired oxygen using an anesthesia gas blender [2 gas reservoirs (21% oxygen, 10% oxygen)] to achieve an arterial oxygen saturation of ~80% SpO₂ (lasting ~2-6 minutes). This will be followed by 2 minutes of normoxic recovery. Ventilation, expired gases, and arterial oxygen saturation (finger pulse oximetry) will be continuously measured. Chemosensitivity will be assessed as the slope of the linear regression line for minute ventilation (L/min), heart rate (beat/min), or blood pressure (mmHg) versus arterial oxygen saturation (%) (Figure 1).

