Expected results, Interpretation, and Follow-up studies: We predict that following 4 weeks of nitrate supplementation compared to placebo, older adults will demonstrate a decrease in blood pressure responsiveness to each of the physiological stressors employed in the lab. Additionally, we hypothesize that dietary nitrate supplementation will have a beneficial effect on central artery stiffness. If our hypotheses are correct, it would suggest a beneficial therapeutic effect of nitrate supplementation in older adults.

General Issues: All techniques in this proposal have been successfully used by [name] for many years and are not expected to present difficulties. Additionally, [name] (Co-investigator) has extensive experience with venous blood draws in humans.

Human Subjects Research

Recruitment of Subjects

The subjects will be recruited from the faculty, staff, and students of the University of Iowa and from persons in Iowa City, Iowa and surrounding communities. Subjects will be eligible based on their health history questionnaire.

Potential Risks.

Risks from participation in these studies are not considered minimal.

1. Venipuncture. Risks of venipuncture in the arm include bruise or clot formation and infection. Additionally, risks associated with a needle stick and blood draws may include feeling light headed or nauseous and/or fainting.

2. Hypoxic ventilatory response tests: The hypoxic ventilatory response will be measured before and after beet root juice supplementation. There are theoretical risks related to prolonged exposure to hypoxia, but acute exposures as planned in this proposal should not pose any risk to the volunteers. Pulse oximetry, blood pressure, capnography, and heart rate monitoring will be used to ensure adequate gas exchange, circulatory parameters, and patient safety when arterial oxygen is altered. We will closely monitor subject arterial oxygen saturation to keep saturation at 70% or higher during the testing. We will have hyperoxia available in the unlikely case saturations fall below 70%.

3. Consumption of Neogenis BeetElite Powder. There is no risk associated with consumption of beetroot juice. However, pink/red urine or stools has been reported.

4. Applanation tonometry. There is no risk associated with arterial tonometry measurements.

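### Does questionnaire-based eligibility, with no written use for the visit-1 pressure, glucose and lipid values, undermine the young-old comparison in Aim 1?

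*Combined protocol and SAP*

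**What the plan says.** Under Research Design and methods, Subjects, the protocol states: "Exclusion criteria include hypertension, hyperlipidemia, smoking, heart disease, diabetes". No numeric criterion is given for the hypertension, hyperlipidemia or diabetes exclusions. The same paragraph excludes a BMI of 30 or more and other conditions that would alter blood pressure responses, and it bars all medication except oral contraceptives in young women. On screening it says: "Subjects will be pre-screened by telephone and a brief health history will be assessed". Recruitment of Subjects adds: "Subjects will be eligible based on their health history questionnaire". The only objective test required before entry is the pregnancy test.

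Three relevant measurements are planned for the testing day:

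- **Blood (Experimental Procedures, item 2):** "Fasting glucose and lipid concentrations will be determined from the blood sample obtained on the first study day"
- **Cuff (item 3):** a brachial cuff pressure calibrates the tonometry waveforms.
- **Nexfin (item 1 and Approach):** beat-to-beat finger pressure is recorded on every study day. Item 4 includes a 10-minute resting period, and the cold pressor item a 2-minute baseline.

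None of these is tied to eligibility. Aim 1 compares young and older adults before any intervention, with the hypothesis: "We hypothesize carotid body chemosensitivity to hypoxia is augmented with healthy aging"

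**The concern.** Self-report misses unrecognised disease, and the no-medication rule removes only drug-treated cases. If unrecognised hypertension, diabetes or hyperlipidemia is commoner in the older group, part of the young-old difference could be disease and not age. Aim 1 has no randomisation to protect it, and no adjustment for pressure, glucose or lipids is described.

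The Background gives reasons to care. It links the chemoreceptors to hypertension and insulin resistance. It also reports that an acute rise in pressure blunts the heart rate response to hypoxia, and heart rate is one of the Aim 1 responses. These two points pull in opposite directions, so the sign of any bias is not settled. The documents do not link hyperlipidemia to chemosensitivity.

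There is a second worry. With one first study day, laboratory values may arrive after the hypoxia tests have been run, so an unwritten rule leaves room to drop subjects with their responses in view.

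**Working it through.** The plan gives no alpha, power, SD, test or prevalence for Aim 1, so there is no figure of its own to reproduce. The calculation below is illustrative.

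**Inputs.** From the protocol: 15 older and 10 young subjects. Assumed: a two-sample t-test at two-sided 5%; 5%, 10% or 20% of older and 0% or 2% of young subjects are unrecognised cases; each case is shifted by d = 0.5 or 1 SD.

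**Precision of the contrast.** SE = √(1/15 + 1/10) = 0.41 SD. With 23 degrees of freedom, the difference detectable with 80% power is 1.19 SD.

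**Bias** = (p_old − p_young) × d.

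| p_young | d | p_old 5% | p_old 10% | p_old 20% |
|---|---|---|---|---|
| 0% | 0.5 | 0.025 | 0.05 | 0.10 |
| 0% | 1 | 0.05 | 0.10 | 0.20 |
| 2% | 0.5 | 0.015 | 0.04 | 0.09 |
| 2% | 1 | 0.03 | 0.08 | 0.18 |

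The largest value is 0.20/1.19 = 17% of the detectable difference and 0.20/0.41 = 0.49 of a standard error. The sign reverses if cases respond less.

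**False-positive rate with no true age effect** (simulated). Two-sided, it is 5.0-5.5% for d = 0.5 and 5.0-6.9% for d = 1. In the direction of the shift alone, where 2.5% is nominal, the rates for p_young = 0 and d = 1 are 3.2%, 4.0% and 6.1% at 5%, 10% and 20%.

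**Chance of at least one case among 15** = 1 − (1 − p)^15 = 54%, 79% and 96%. One case moves the older mean by only d/15: 0.5/15 = 0.03 SD or 1/15 = 0.07 SD.

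**Harsher assumptions** (fixed number of cases, mean shift only, noncentral t). Three cases at 1.5 SD give a bias of 3/15 × 1.5 = 0.30 SD and a rejection rate of 10.9%. Five cases at 1.5 SD give 0.50 SD and 21.7%.

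**Cost of a formal visit-1 check.** Dropping older subjects from Aim 1 without replacement raises the detectable difference to 1.21, 1.24 or 1.26 SD with 14, 13 or 12 left. Power for 1.19 SD falls from 80% to 79%, 77% or 76%. The crossover would lose more if those subjects left it too: a paired t-test set at 80% power with n = 15 falls to 77%, 73% or 69% at n = 14, 13 or 12.

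**The case for a change.** The strongest argument for a change is that the textual gap is real and cheap to close. A health check with no written criterion and no stated action cannot be applied uniformly. Aim 1 depends on the older group being healthy, and the Background itself calls the literature on aging and chemosensitivity inconclusive. The two-sided error rate also understates the effect: in the direction of the shift, the rate more than doubles at the upper end (2.5% to 6.1%). Nothing in the documents rules out the harsher assumptions.

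Much of this stands. The gap exists in the text that can be read, although the figure showing the testing day is not available. The word modest is a judgement about assumed inputs, not a result from the documents.

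What does not stand is the need for an amendment. Glucose and lipids are drawn once, on the first study day, and have no other stated use; confirming or describing health status is the obvious purpose. Resting Nexfin pressure is recorded in both age groups, so pressure data exist for the young even if no cuff reading was planned. Analysts can tabulate these values by age group and see whether the groups were healthy. A formal rule has drawbacks of its own. A single-visit reading would define the main Aim 1 set and could remove healthy people. It would need written criteria and an assessor unaware of the responses. It would also act on older subjects who, by the Dietary Nitrate Supplementation item, are randomised on entering the study.

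**Conclusion.** No change to the plan follows. The protocol leaves unsaid how measurements it already collects relate to three of its exclusions, and a sensible analyst fills that gap when describing the two groups at baseline. The stricter remedy, removing subjects on visit-1 values, is a trade-off that could cost the crossover more power than it costs Aim 1.

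The possible harm is confined to Aim 1, a secondary contrast in a study meant to supply preliminary data for a larger trial. With 5-20% of older subjects affected and shifts of 0.5-1 SD, the bias is at most 0.20 SD, about half a standard error, and the two-sided error rate stays between 5.0% and 6.9%. Every prevalence and shift is assumed and the direction is open. A materially larger distortion needs several unrecognised cases, each shifted by more than 1 SD. In the active-versus-placebo comparison each older subject is their own control, so unrecognised cases affect whom the result applies to and its variability, but do not bias it.
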